9.8. SPONSOR INVESTIGATOR RESPONSIBILITIES

The Sponsor-Investigator will review documented serious adverse effects and abnormal test findings to determine 1) if the abnormal test finding should be classified as an adverse effect; 2) if there is a reasonable possibility that the adverse effect was caused by the investigational device or, if applicable, other study treatment or diagnostic product(s); and 3) if the adverse effect meets the criteria for a *serious adverse effect*.

In accordance with 21 CFR Part 812.150(a)(1) and (b)(1), the sponsor shall promptly report the results of an evaluation of any serious and unanticipated adverse device effect to FDA, the University of Michigan IRBMED and participating investigators (if any) as soon as possible, but not later than 10 working days after the sponsor first receives notice of the effect. Thereafter, the sponsor shall submit such additional reports concerning the effect as the FDA requests. Complications and non-serious or anticipated adverse events should be documented and tabulated but need not be submitted by the sponsor to the FDA as individual reports.

10. DEVICE ACCOUNTABILITY

All use of the SCD will be under the direct supervision of the principal investigator or his/her designee. The investigational devices will be clearly labeled as investigational use only and have a clearly marked serial number for each device. The receipt date and lot number will be recorded, and package sterility confirmed. The devices will be stored in a secure location with access limited to the study team.

All records of receipt, use, and disposition of the devices will be maintained by the study team. At the completion of the study, there will be a final reconciliation by study personnel of devices shipped, used, and devices remaining. Any discrepancies noted will be investigated, resolved, and documented prior to return or destruction of unused devices.

11. DATA SAFETY MONITORING BOARD

An independent Data Safety Monitoring Board (DSMB) will review safety results over the course of the study on a schedule set by Drs. [name] and [name] and the DSMB. The DSMB will comply with the FDA Guidance: "Guidance for Clinical Trial Sponsors on the Establishment and Operation of Clinical Trial Data Monitoring Committees". The DSMB will be formed to provide scientific and medical feedback for the study.

The DSMB will focus on the following areas:

- Performance* – to assess study conduct and compliance
- Effectiveness* – to assess mortality and dialysis dependency
- Safety* – to assess the incidence, severity, relationship, and timing of adverse events and to identify safety concerns; and
- Context* – to assess the study relative to the AKI literature.

The DSMB will reflect the disciplines and medical specialties necessary to interpret the data from the clinical study and to fully evaluate participant safety. The SCD-PED-02 DSMB will be made up of at least 2 medical practitioners with expertise in AKI and critical care medicine. The DSMB will operate under a charter and will identify prospective data display specifications to conduct independent data reviews. The DSMB will make recommendations to the Sponsor to continue the study as planned or to stop the study due to safety. The DSMB will meet to perform safety evaluations and to provide feedback to the Sponsor Investigator at least quarterly. The DSMB reserves the right to request more frequent evaluations.

12. PROTOCOL ANALYSIS / SCIENTIFIC SOUNDNESS

This study derives from the hypothesis that up to ten or less sequential 24 hour SCD treatments will improve survival in patients with AKI requiring CRRT as compared to historical data. Further, SCD therapy may reduce the duration of maintenance dialysis secondary to acute renal failure (ARF) due to acute kidney injury (AKI).

The precise mechanism of action of the SCD is becoming better understood and appears to be an immunomodulatory process which inhibits leukocyte activation, a trigger of systemic inflammatory response syndrome (SIRS) and multi-system organ failure. The modulation of the pro-inflammatory state is believed to also allow recovery of renal function in AKI and other organ failure. The cartridge in

the presence of citrate anticoagulant acts as a selective cytoprotective device to sequester and inhibit potentially damaging circulating leukocytes.

Recent data have demonstrated, that the inflammatory response of neutrophils adhered to a [REDACTED] membrane in the presence of low iCa and citrate are released with a normalized apoptotic life span, compared to a delayed apoptotic rate promoted in systemic inflammation. Leukocytes, especially neutrophils, are major contributors to the pathogenesis and progression of clinical inflammatory disorders, including SIRS, sepsis, ischemia/reperfusion injury and ARDS. Further data have demonstrated that monocytes with a proinflammatory phenotype, binds more avidly than monocytes with a reparative phenotype to the membrane in low iCa environment. This selective binding results in a less inflammatory circulating monocyte population in disorders of inflammation. The protocol has been carefully constructed with precise AKI diagnostic criteria, CRRT or comparable mode treatment and definition of patient's age, need to tolerate citrate anticoagulation and placement in the ICU during SCD therapy. Subject exclusion criteria are also detailed so as to provide a well characterized and standardized subject population. Observational periods and a complete schedule of events in the protocol delineate specific efficacy measurements as required to test the study hypothesis, including bio-inflammatory assay markers, and WBC activation studies.

Besides the test of the hypothesis the study is focused on observable, empirical and laboratory determinations of subject safety while on the SCD. Previous human trials have been conducted on the SCD device and the protocol contains a review of AE and SAE data from all SCD human studies and findings from those studies contributed to constructing the investigative safety profile. Safety endpoint measures specified in the protocol include adverse events, laboratory safety parameters, vital signs, ventilation status and hemodynamic variables. Device integrity and performance measurements are also defined as are circumstances which demand premature termination of SCD treatment.

Prolonged exposure to the SCD is anticipated to result in superior outcomes, although as noted above, this pilot study is not designed to assess for efficacy. However, we understand that a minimum amount of exposure to the SCD will be required for an appropriate safety analysis and for making any inference regarding efficacy. The ppCRRT experience demonstrated that the majority of patients (201/370) received CRRT for 1 to 7 days and exhibited 65% survival (Symons et al CJASN 2007 Table7).

This trial is an early safety efficacy study but is not powered for statistical significance. Insights into a comparison of historical controls matched to SCD treated subjects will utilize the ppCRRT Registry to match for: etiology of AKI, co-morbidities, CRRT modality, dose and form of anticoagulant, adverse events. [10]

The ppCRRT Registry has data fields for the primary reason for CRRT, including AKI and its cause, as well as co-morbidities which will be matched for primary organ system involvement. The CRRT modality was evenly distributed between convective and diffusive modality, with 60% of the convective modalities provided as CVVH and 40% as CVVHDF. The anticoagulant protocol will be standardized with ACD-A/CaCl₂ and all centers used the same protocol in ppCRRT Registry as outlined in this study protocol. Thus, the ppCRRT Registry dataset will be able to be matched to our study subject cohort. Also as noted above, subjects will be matched for age, size and PRISM II score.

The Prospective Pediatric CRRT (ppCRRT) database will be used as a control for the CRRT treatment related factors including: patient age, gender, primary cause of AKI, total treatment duration, CRRT modality (CVVH, CVVHD, CVVHDF), CRRT small solute clearance (ml/1.73m²/hour), baseline estimated GFR (using the original Schwartz formula, which was used in the ppCRRT), urine output in the 24 hours prior to CRRT initiation (ml/kg/hour), percent fluid overload at CRRT initiation based on admission ICU weight, vasoactive medication number at time of CRRT initiation and mean airway pressure at CRRT initiation.

An additional analysis will also evaluate patients who have achieved targeted iCa levels during 90% of treatment time and those who do not.

In summary this protocol meets all criteria necessary for clinical scientific inquiry related to a test of hypothesis in a well monitored environment focused on subject safety during the conduct of the study. Basic statistics will be performed on the data sets along with historical data comparisons and subjected to subset analysis where appropriate. The results will help to guide the design of a future pivotal study of this device.

The rational for therapy, study objectives and endpoints, design, inclusion and exclusion criteria are explicitly defined. Subject safety parameters are well documented including safety reporting, safety observations and assays, procedures for subject withdrawal and study discontinuation criteria along with monitoring device integrity and performance. Lastly, a review of all prior SCD human study safety data is included in the protocol for full disclosure to study investigators and the informed consent document includes a full description of all known and potential risks of the device treatment.

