5. SELECTION OF PATIENT POPULATION

5.1 STUDY POPULATION

Up to 10 pediatric patients with a clinical diagnosis of AKI requiring CRRT will be enrolled in this study, in up to 7 Clinical Centers in the United States.

Pediatric patients with a body weight (BW) between ≥ 10 and ≤ 20 kg receiving care in the Intensive Care Units of each participating hospital will be screened daily and identified for participation in the trial.

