7. TREATMENT INTERRUPTIONS – DISCONTINUATION CRITERIA

7.1. TREATMENT DISCONTINUATION CRITERIA

Subjects may be withdrawn from therapy prior to hour 240 for a variety of reasons. When therapy is discontinued prior to hour 240, the follow-up period will immediately begin and data will continue to be collected per protocol.

The Principal Investigator will assign a primary reason for therapy termination utilizing the categories listed in 7.2 and 7.3 below, and if appropriate, one or more subcategories. The Principal Investigator will notify the Sponsor or designee within 24 hours of withdrawal of participation.

7.2. CLINICAL CRITERIA:

1. Improvement in Clinical Status

If a subject's condition improves (e.g. renal condition has improved to the extent that CRRT can be discontinued or hemodynamic status has improved so that the dialysis modality can be changed from CRRT to IHD) treatment may be discontinued before the 240 hour treatment period. The decision to discontinue treatment based upon improvement in clinical status will be made by the Principal Investigator.

2. CRRT related events

Such as inability to maintain vascular access based upon PI's clinical assessment. Includes failure of the CRRT device and/or circuit that requires treatment to be discontinued prior to hour 240 of therapy.

3. SCD related medical events

Such as persistent leukopenia, neutropenia or thrombocytopenia based upon PI's clinical assessment of relationship to SCD.

4. SCD Failure/Malfunction

Any failure of the SCD that requires treatment to be discontinued prior to hour 240 of therapy e.g. clotting or evidence of leakage in the SCD or inability to maintain a patent circuit.

5. Death or withdrawal of life support**6. Regional Citrate Anticoagulation Intolerance**

All subjects must be able to tolerate and achieve satisfactory regional citrate anticoagulation. Tolerance of regional citrate anticoagulation is defined as achieving:

- Two (2) consecutive circuit ionized calcium levels of < 0.40 mmol/L (or < 1.6 mg/dL),
- At least 30 minutes apart, and
- Within the first 12 hours of SCD initiation.

If unable to achieve the specific circuit ionized calcium levels within the time frame above, treatment with the SCD must be discontinued. The subject will progress on to the post-SCD follow up period, unless the subject and/or legal guardian withdraws consent for the study.

7. Hematologic Events

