9.7.2. TREATMENT PERIOD THROUGH END OF STUDY

All adverse events that occur from the time of SCD start will be recorded as follows:

- Serious Adverse Events (identified in **Section 9.2**) will be recorded until Day 60 after enrollment, death, or subject withdrawal of study consent, whichever occurs first.
- Non-serious adverse events will be recorded until end of 120 hours after the SCD Treatment Period ends, death, subject withdrawal of study consent or until ICU discharge, whichever occurs first.

Any serious adverse event (regardless of relationship to the

treatment) occurring from the time of enrollment through end of study must be reported to the CCC and DCC at Cincinnati Children's Hospital, within 24 hours of knowledge of the event.

Each clinical trial site will be supplied with written SAE reporting instructions, SAE reporting forms and contact information for reporting of serious adverse events.

For any AE that is ongoing at the time of the initial report, periodic follow-up information will be required until the adverse event is resolved or the patient is no longer in the study, whichever occurs first.

The Investigator is responsible for all adverse events reporting to the Institutional Review Board (IRB) according to the requirements of the IRB and for providing clinical trial monitors with all medical records needed to source-verify the adverse events.

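### Section 12 requires an unspecified minimum SCD exposure for the safety analysis, and no analysis set is defined, so excluding children who stop early is not ruled out

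*Combined protocol and SAP*

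**What the plan says.** Section 12 (Protocol Analysis / Scientific Soundness) states that "a minimum amount of exposure to the SCD will be required for an appropriate safety analysis and for making any inference regarding efficacy". No number of hours, days or cartridges is attached, and the text does not say whether children below the minimum are excluded, replaced or summarised separately. The sentence before it begins "Prolonged exposure to the SCD is anticipated to result in superior outcomes" and goes on to say that the pilot is not designed to assess efficacy. The sentence after it reports that in the pediatric CRRT registry "the majority of patients (201/370) received CRRT for 1 to 7 days and exhibited 65% survival".

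On size and purpose, Section 5.1 says "Up to 10 pediatric patients with a clinical diagnosis of AKI requiring CRRT will be enrolled in this study", and Section 12 adds "This trial is an early safety efficacy study but is not powered for statistical significance". Section 4 describes the study as open-label.

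The collection rules carry no exposure condition. Section 9.7.2 says "All adverse events that occur from the time of SCD start will be recorded as follows", and serious events "will be recorded until Day 60 after enrollment, death, or subject withdrawal of study consent, whichever occurs first". Under Section 7.1 a child whose treatment ends before hour 240 moves straight into follow-up and data collection continues. The earliest mandatory stop is in Section 7.2, item 6, on citrate tolerance in the first 12 hours: "If unable to achieve the specific circuit ionized calcium levels within the time frame above, treatment with the SCD must be discontinued". That child also moves to follow-up unless consent is withdrawn.

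**The concern.** The primary objective is safety. In a study of this kind the natural safety population is everyone in whom the device was started, because harm can end exposure. Several of the discontinuation reasons in Section 7.2 are themselves safety or device outcomes: death, clotting or leakage, cytopenia, and failure to reach the citrate target. A minimum-exposure condition makes inclusion depend on something that happens after treatment starts and is tied to outcome.

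With no threshold and no analysis set, the choice of minimum would be made by people who already know who died, who clotted and who stopped. With at most 10 children, moving one or two of them in or out changes every reported proportion by several percentage points. The same choice would carry over into the comparison with registry controls.

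**Working it through.** **Step 1. Figures to reproduce.** The documents state no minimum, alpha, power or effect size. The only number beside the sentence is the registry fraction: 201/370 = 0.543, so calling it a majority is correct. It describes CRRT duration in the registry and is not offered as an SCD minimum. Because it is a duration per patient, it does favour reading the minimum as applying to each child.

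**Step 2. The provisions side by side.**

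| Provision | Section | Governs | Says whose data are analysed? |
|---|---|---|---|
| Events recorded from SCD start; serious events to Day 60 | 9.7.2 | Collection | No |
| Causality assessed for all enrolled children | 9.5 | Assessment | No |
| Events expressed relative to device exposure time | 9.7 | Metric | No |
| Early stoppers enter follow-up | 7.1; 7.2 item 6 | Collection | No |
| Day-28 renal recovery in children alive at day 28 | 3.2 | One endpoint | Yes, by survival and not by exposure |
| Calcium target met for 90% of treatment time, or not | 12 | One additional analysis | Yes; both groups are kept |
| Minimum SCD exposure | 12 | Safety analysis and efficacy inference | A condition without threshold or handling rule |

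**Step 3. Who has short exposure.** Section 7.2 lists improvement (item 1), SCD-related medical events (3), SCD failure (4), death or withdrawal of life support (5), citrate intolerance (6) and hematologic events (7). A child who misses the citrate target stops at about hour 12 of a possible 240, and 12/240 = 5%. If the minimum were set at one full 24-hour treatment, an assumed value, all such children would fall below it.

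**Step 4. Effect on mortality (illustration).** Let D children die among N, and let a cut-off remove d of the deaths and r of the survivors.

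- Mortality after the cut-off = (D − d)/(N − d − r).
- This is below D/N exactly when d/(d + r) > D/N, that is, when deaths are over-represented among the children removed.

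Inputs: N = 10 (Section 5.1). D = 3, 4 or 5 is an assumption. It brackets 100% − 65% = 35% (the registry survival in Section 12) and the approximately 50% mortality in the synopsis rationale. The values of d and r are assumptions, because the documents give none.

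Only early deaths removed (r = 0):

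| D | All kept | d = 1 | d = 2 | d = 3 |
|---|---|---|---|---|
| 3 | 3/10 = 30% | 2/9 = 22% | 1/8 = 12.5% | 0/7 = 0% |
| 4 | 4/10 = 40% | 3/9 = 33% | 2/8 = 25% | 1/7 = 14% |
| 5 | 5/10 = 50% | 4/9 = 44% | 3/8 = 38% | 2/7 = 29% |

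Each death removed lowers mortality by between 5.6 points (50% to 44.4%) and 12.5 points (12.5% to 0%). The Clopper-Pearson 95% intervals are wide throughout: 12% to 74% for 4/10 and 3% to 65% for 2/8.

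Early recoverers removed as well: with D = 4, d = 1 and r = 2, mortality is 3/7 = 43%, above the 40% with everyone kept. The rule agrees, since d/(d + r) = 1/3 = 33% is less than 40%.

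**Step 5. Effect on safety.** The number of children with a given event can only fall or stay the same when children are dropped. If one child in 10 stops for clotting and is excluded, 1/10 becomes 0/9. For an event seen in nobody, the one-sided 95% upper bound is 1 − 0.05^(1/n): 25.9% at n = 10, 31.2% at n = 8 and 34.8% at n = 7.

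**The case against.** The strongest reply is that the sentence is not an analysis rule. It has no threshold, so nothing can be applied, and it can be read as a remark that the pilot needs enough total exposure to be informative. The operative safety provisions point towards including everyone: recording starts with SCD, causality is assessed for all enrolled children, early stoppers stay under observation, and clotting and leakage are endpoint criteria in their own right.

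Much of this stands, and it rules out several stronger readings that a reader might infer:

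- *That the plan will drop early deaths and early failures.* No exclusion instruction is written.
- *That this is the only statement on who is analysed.* Section 3.2 (day-28 renal recovery) and Section 12 (the calcium-target analysis) each contain one.
- *That a cut-off must flatter mortality.* Improvement is the first discontinuation reason in Section 7.2, so early recoverers could be dropped too and the net effect can go either way.
- *That registry controls have no comparable filter.* Section 12 lists total treatment duration among the registry control factors. Duration is itself known only after treatment starts, so using it does not remove survivor bias, but a flat claim of unfiltered controls is unsupported.
- *That the expectation of better results with longer exposure is a biased estimate.* It is an expectation, qualified in the same sentence, and no exposure-outcome analysis is planned.
- *That this is a first-use study.* Section 2.6 describes an earlier pediatric study with 16 children enrolled and an overlapping weight range.

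What does not stand is the inference from collection to analysis. Complete data can be collected and then left out of a summary. None of the safety provisions names an analysis population, and the one sentence that links exposure to the safety analysis states a requirement.

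**Conclusion.** The point holds in a limited form. An undefined minimum exposure is stated as a requirement for the safety analysis and for efficacy inference, no analysis set is defined, and a cut-off chosen after outcomes are known is therefore not ruled out. The exposed result is the primary one, safety, because early deaths, clotting, cytopenia and citrate failures are among the short exposures.

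The size cannot be computed from the documents. If only early deaths were dropped, and 3 to 5 of 10 children died, mortality would fall by about 6 to 12.5 points per child removed. If early recoverers were dropped as well, it could rise. These figures rest on assumed counts and show sensitivity, not an expected bias. The study is unpowered, so no formal test is at risk, but its results are meant to guide a pivotal design. That is enough reason to settle the denominators now.

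**What to change.** Replace the minimum-exposure sentence in Section 12 with:

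*All children in whom SCD is started, for any duration, are included in the safety and device-integrity analyses. All enrolled children are included in the mortality and dialysis-dependency outcomes.*

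Add that any exposure-restricted summary is supplementary, is labelled as such and uses a threshold stated in advance. If that summary is compared with the registry, an equivalent duration and survival condition is applied to the controls. The reporting of events relative to exposure time in Section 9.7 already handles unequal exposure and needs no change.

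The cost is a few sentences. No new data are needed, because the collection rules already cover these children. Mortality or event counts may look slightly less favourable than under a restricted summary. If the sponsor only meant that the study needs enough total exposure, the change costs nothing.

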5.3 EXCLUSION CRITERIA

1. Threshold blood pressure of 80/40 mmHg-- patients with both a systolic blood pressure of less than 80 mmHg and a diastolic blood pressure of less than 40 mmHg.
2. Patients with a solid organ transplant or those with a bone marrow or stem cell transplant in the previous 100 days or who have not engrafted.
3. Acute or chronic use of circulatory support device, other than ECMO, such as LVADs, RVADs, BIVADs.
4. Presence of preexisting advanced chronic renal failure (i.e., ESRD) requiring chronic renal replacement therapy prior to this episode of acute kidney injury or with pre-existing chronic kidney disease (CKD) defined as a eGFR<30 ml/min/1.73m². Patients who have never seen a pediatric nephrologist will be assumed not to have pre-existing CKD.
5. AKI occurring in the setting of burns, obstructive uropathy, scleroderma renal crisis, atheroembolism, functional or surgical nephrectomy, cyclosporine or tacrolimus nephrotoxicity.
6. Metastatic malignancy which is actively being treated or may be treated by chemotherapy or radiation during the subsequent three month period after study therapy.
7. Chronic immunosuppression with the exception of corticosteroids up to a dose of 10 mg per day.
8. Known positive HIV or AIDS or COVID-19
9. Current Do not Attempt Resuscitation (DNAR), Allow Natural Death (AND), or withdrawal of care status, or anticipated change in status within the next 7 days.
10. Patient not expected to survive 28 days because of an irreversible medical condition. (This is not restrictive to AKI, and may include situations such as the presence of irreversible brain damage, untreatable malignancy, inoperable life threatening condition, or any condition to which therapy is regarded as futile by the PI.)

11. Any medical condition that the Investigator thinks may interfere with the study objectives.
12. Treating clinician does not feel it is in the best interest of the patient.
13. Platelet count <15,000/mm³.
14. Concurrent enrollment in another interventional clinical trial.
Patients enrolled in clinical trials where only measurements and or samples are taken (NO TEST DEVICE OR TEST DRUG USED) are allowed to participate.
15. Use of any other investigational drug or device within the previous 30 days.
16. Use of AN-69 hemofilter membranes

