6.4 BASELINE PERIOD

The Baseline Period begins at enrollment and ends at the start of the SCD Treatment Period (when the subject starts treatment). The following information will be recorded as close to the start of the SCD Treatment Period as possible. Data from standard of care tests may be used as baseline data, as long as it is captured within the time frames noted.

- **Demographic Data**
 - a) Date of birth
 - b) Gender
 - c) Race/ethnicity
- **Hospitalization Data**
 - a) Hospital Admission Date
 - b) Hospital Admission Diagnosis
 - c) ICU Admission Date
 - d) ICU Admission Diagnosis
 - e) Medical History
- **Vital Signs/Physical Assessment (within 12 hours prior to the start of SCD Treatment Period unless otherwise indicated)**
 - Temperature
 - Blood Pressure and heart rate
 - Body weight at ICU admission
 - PRISM II Score
 - Physical Exam
 - Urine Output (previous 24 hours)
 - ICU percent fluid overload at CRRT initiation (Defined as [(Fluid In (liters) – Fluid Out (liters))/ICU admission weight (kg)] x 100% where Fluid In and Fluid Out are calculated from ICU admission to CRRT initiation.
- **Clinical Laboratory Tests (within 12 hours prior to the start of SCD Treatment Period)**
 - CBC with differential
 - BUN/Creatinine
 - Na, K, Cl, HCO₃, Ca, Mg, Ionized Ca, PO₄
 - ALT, AST, Bilirubin, ALP, Total Protein, Albumin, Glucose
- **Respiratory**
 - Status – Ventilator support (yes/no; date of intubation)
 - If on Vent: FiO₂
 - If on Vent with an arterial line: Arterial Blood Gas (12 hours prior to start of SCD Treatment Period)
 - If on Vent without an arterial line: Arterial Blood Gas (if available within 12 hours of start of Observation Period per standard of care)
 - ECMO Status (yes/no; date of cannulation)
- **Blood for Research**
 - Blood sample should be collected within 6 hours before the start of the SCD Treatment Period

- Blood sample will be sent to an outside laboratory for testing of biomarkers. The research laboratory is Innovative BioTherapies located at [name].
- **Other (Event-driven)**
 - Acknowledgement (yes/no) to critical medications, vasopressors, and blood products administered to the patient in the 24 hours prior to start of SCD Treatment Period
 - Adverse Events occurring since enrollment
 - Microbiology/culture data (within the last 72 hr.)

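### ECMO is permitted and recorded but is in none of the registry matching or control lists, so an ECMO child may be compared with a non-ECMO control

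*Combined protocol and SAP*

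**What the plan says.** **Eligibility.** Exclusion 3 in Section 5.3 reads "Acute or chronic use of circulatory support device, other than ECMO, such as LVADs, RVADs, BIVADs". ECMO is thus the one form of circulatory support expressly allowed. Section 6.2.3 and Appendix F describe how the device is placed in a combined CRRT and ECMO circuit.

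**Data collection.** The baseline list in Section 6.4 includes "ECMO Status (yes/no; date of cannulation". ECMO is also a row in the Section 6.3 schedule and is recorded during treatment (Section 6.5) and in the post-treatment period (Section 6.6.1).

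**Comparison.** The synopsis evaluation plan sets mortality and dialysis dependency against historical controls, and Section 3.1 writes that comparison into the primary objective. Section 12 describes the registry controls in two ways, the first of which also appears at the end of Section 3.2:

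- Matching: "match for: etiology of AKI, co-morbidities, CRRT modality, dose and form of anticoagulant, adverse events". Co-morbidities are handled as "co-morbidities which will be matched for primary organ system involvement", and the text adds "Also as noted above, subjects will be matched for age, size and PRISM II score".
- Control: the registry "will be used as a control for the CRRT treatment related factors including: patient age, gender, primary cause of AKI, total treatment duration", followed by modality, clearance, baseline GFR, urine output, fluid overload and finally "vasoactive medication number at time of CRRT initiation and mean airway pressure at CRRT initiation".

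ECMO is in neither list, and no stratum, subgroup or sensitivity analysis by ECMO status is named.

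**The concern.** A historical comparison is only as good as the baseline factors on which the two groups are made alike. Here a form of organ support that the protocol singles out in eligibility, circuit design and data collection is missing from those factors. With up to 10 children, each contributes 10 percentage points to the observed mortality, so a few pairs that are unlike on ECMO could move the contrast. The study is descriptive, but Section 12 says its results will help to guide a pivotal design, so an avoidable imbalance in the comparison is worth removing.

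**Working it through.** **Step 1. Is ECMO covered indirectly?** The measures that might stand in for it are PRISM II, the number of vasoactive drugs and mean airway pressure.

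- Section 6.2.3 says that children who need CRRT on ECMO almost always come to need it after at least 24 hours of ECMO.
- Section 6.4 places PRISM II within 12 hours before device treatment starts. Section 12 takes the vasoactive count and mean airway pressure at CRRT initiation.
- In a child on ECMO, all three would therefore usually be taken while ECMO is running.
- Appendix A scores PRISM II partly on blood pressure, heart rate and gas exchange, which are functions that ECMO supports.

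That these measures may then fail to stand in for ECMO is a clinical inference from timing and content. Matching co-morbidity by primary organ system does not separate an ECMO child from a non-ECMO child with the same organ involved.

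**Step 2. Could it arise with 10 children?** The ECMO share among eligible children is not in the documents. For an assumed share *s*, P(at least one of 10) = 1 − (1 − *s*)^10:

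- *s* = 10%: 1 − 0.9^10 = 65%
- *s* = 20%: 1 − 0.8^10 = 89%
- *s* = 30%: 1 − 0.7^10 = 97%

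**Step 3. How large could the shift be?** The plan states no figure for this, so there is none to reproduce. Suppose *k* of 10 study children are on ECMO and all controls are non-ECMO. Then

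shift in expected control mortality = (*k*/10) × (*m*_ECMO − *m*_non)

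Inputs:

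- *m*_non = 35%, a stand-in. It is 100% − 65%, from the survival that Section 12 quotes for registry patients with 1 to 7 days of CRRT (201/370 = 54.3% of the registry). That group is not described as non-ECMO.
- *m*_ECMO = 35% to 70%, assumed.
- *k* = 0 to 5, assumed.

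| *k* of 10 | *m*_ECMO 35% | 45% | 60% | 70% |
|---|---|---|---|---|
| 0 | 0 | 0 | 0 | 0 |
| 1 | 0 | 1.0 | 2.5 | 3.5 |
| 3 | 0 | 3.0 | 7.5 | 10.5 |
| 5 | 0 | 5.0 | 12.5 | 17.5 |

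Entries are percentage points; for example 0.3 × (60 − 35) = 7.5.

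**Step 4. Which way?** In this set-up, if ECMO carries excess mortality, control mortality is too low and the device looks worse. If the chosen controls include more ECMO than the study children, the sign reverses. The documents give neither share.

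**Step 5. Against random error.** For 3 deaths in 10, the exact 95% interval is 6.7% to 65.2%, which is 23.3 points below and 35.2 above the estimate. The largest shift in the table, 17.5 points, is smaller than either arm.

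**The case against.** **The lists are not closed.** The control list is introduced by a word that makes it illustrative, it may mean adjustment rather than matching, and Section 12 leaves room for subset analyses. All true. But none of this names ECMO, and adding it once the outcomes of 10 children are known would be a post hoc choice.

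**The study is small and unpowered.** Section 12 says so itself, and random error is larger than the likely bias. This stands, and it is why the point is minor. It does not remove the point: a confidence interval does not reflect an imbalance of this kind.

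**The registry may not hold ECMO status.** The documents do not say. Matching therefore cannot be the only remedy.

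**The form may not capture the right moment.** Section 6.4 records status close to the start of device treatment, and CRRT may begin earlier (Section 6.3, note 5). A child who came off ECMO in between could be missed. This stands and limits how exactly status at CRRT initiation can be established.

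**Stronger readings that the documents do not support.** A reader might infer that ECMO children would be paired with less ill controls, biasing the comparison against the device. No section says that ECMO lowers the listed measures or that it is a strong predictor of death. Appendix A also scores coagulation, bilirubin, neurological status and blood chemistry, so it is not shown that the PRISM II total reads too low. A reader might also infer that pooling safety data across ECMO and non-ECMO circuits is unsound. Section 6.2.3 does leave priming on ECMO to the treating team, and Appendix E exempts ECMO from its priming recommendation. But Section 6.2.3 also says that the added volume and the pressure gradients are not a problem and that the device sees similar pressures. That supports identifying these children in listings, not a finding that the pooled data are invalid.

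**Conclusion.** The omission is real: ECMO is allowed and recorded, but nothing in the matching or control lists prevents an ECMO child from being compared with a non-ECMO control. Whether this biases the result, and in which direction, cannot be settled from the documents. The 0 to 17.5 point range rests on an assumed ECMO share and an assumed ECMO mortality, with 35% as a stand-in for the rest. It includes zero, which is the answer if no ECMO child is enrolled or if ECMO carries no excess mortality. The point is minor. It is worth acting on because the trial already collects the variable, not because the effect is known to be large.

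**What to change.** In Section 12, and in the parallel text in Section 3.2:

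1. Add baseline ECMO status (yes/no, as recorded before device treatment starts) to the matching factors if the registry holds it. Use the cannulation date to establish status at CRRT initiation where possible.
2. Whether or not the registry holds it, show the mortality and dialysis comparison with and without the ECMO children.
3. Flag ECMO status in the adverse event and laboratory safety listings. Separate rates are not needed, since they would rest on very few children.

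**Cost.** A wording change, one extra presentation of the comparison and a check of the registry's fields. No new trial data are needed. The downside is that some ECMO children may have no match, and the comparison without them rests on fewer than 10 children if any are enrolled.
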